1) Male or female, ages 18-65; 2) medically stable; 3) >6 months post-SCI; 4) SCI affecting segments between C4-T12; 5) no other known neurological disorders; 6) no severe musculoskeletal impairments, open wounds, or skin lesions that would limit participation in functional assessments; 7) able to provide informed consent

Exclusion criteria:

1) Not meeting any of the above inclusion criteria; 2) presence of a self-reported uncontrolled medical condition including, but not limited to: cardiovascular disease; sleep apnea; obstructive lung disease; severe neuropathic or chronic pain; severe recurrent autonomic dysreflexia; 3) severe, untreated bladder or urinary tract infection; 4) women who report being pregnant or test positive on a pregnancy test.

We aim to screen 40 individuals with SCI and enroll 30 subjects in this study.

Recruitment and enrollment

The target population will be individuals with SCI. Study procedures will take place at Brooks Rehabilitation in Jacksonville, FL, and the University of Florida's Health Science Center Department of Physical Therapy Research Laboratories. Subjects will be recruited in four ways.

- 1) The study team will notify Brooks clinicians about the study via e-mail. The study team may also notify other clinicians who work with individuals with SCI through e-mail. Those clinicians may then notify their patients about the study, who may then contact [name], the principal investigator, or other study staff for more information.
- 2) Potential subjects also may be informed of the study via IRB approved flyers, which will be hung in the Brooks Health System, the Health Science Center at UF, and in the community. Contact information will be provided on the flyer so that interested potential subjects may contact [name] for more information.
- 3) Information regarding the study also may be provided through word of mouth or general presentations such as at support groups and community meetings (i.e. such as meetings for those with SCIs).

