A standardized and reliable protocol using a hand-held force dynamometer will be used to assess postural muscle strength for maintaining upright sitting (Larson et al., 2010). A study staff member will apply force to the participant's chest (anterior strength), upper back (posterior strength), or either shoulder (lateral strength) while the participant is asked to resist the force to remain seated, unsupported, on a mat table. The force applied at the point that the participant loses balance or can no longer sit unsupported will be recorded as strength in that direction. This test of seated strength will be carried out by a study staff member experienced in administering the test, and the participant will also be spotted by an additional therapist or research assistant in case the participant is unable to balance themselves during the test.

3c) Assessments of ambulation

These are standard, clinical tests of functional ability that may be used to assess mobility in subjects who can safely attempt these tests. Outcomes from these assessments will allow us to quantify the level of functional mobility of our subjects, and if acute intermittent hypoxia affects levels of functional mobility. These assessments may include:

- a) Timed Up and Go Test – Assessment of walking balance, and fall risk based on the participant's ability to stand up from a seated position, walking 10 meters, turn around and return to the chair and sit down.
- b) 10 meter walk test – Assessment of walking speed over a distance of 10 meters
- c) 30 second chair stand test – Assessment of lower body strength and power in mobility impaired populations, by assessing the maximum amount of times that a participant can safely stand up from a seated position in 30 seconds.

4) EMG activation and activation patterns of respiratory, postural, and lower extremity muscles

Muscle activity will be collected and measured by surface EMG. By analyzing the electrical activity generated during a muscle contraction, EMG analyses allow us to understand timing and amplitude of muscle activation as well as the frequency content of the EMG signal. Thus, we will be able to assess how the nervous system's control of

muscles is disrupted following SCI, and whether this control will be affected by acute intermittent hypoxia.

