Using standard surface preparation (cleaning the skin with water or alcohol pad, shaving of excess hair) and electrode placement, EMGs will be collected from postural muscles of the trunk, accessory respiratory muscles, and lower extremity muscles using surface EMG electrodes. EMG sensors will be attached to the skin with hypoallergenic medical tape. Before data collection, tests of each EMG channel may be performed to ensure clear signals and to check for crosstalk. EMG information will be used to assess when different postural, respiratory, or lower extremity muscles fire during the assessments, as well as when certain muscles fire in relation to one another.

5) Trunk positioning and function using non-invasive sensors.

Electrogoniometers may be placed on the hips, knees, or spinous process on the back of subjects to allow for quantification of the angle of the spine or hips achieved during each task. These sensors will be attached to the skin using double-sided, medical grade, hypoallergenic tape. Information gained from these movement sensors will allow for quantification of how a subject performs respiratory tests and postural muscle functional tasks.

Very thin, light pressure sensors made of flexible plastic may be worn in the subjects' shoes, under their heels and/or the ball of their feet. As the subjects will be seated with their feet on the ground during the tests of postural muscle function, the non-invasive pressure sensors may help give an idea of how much force the subject is imparting on the ground during different tasks. Since the seated tasks of postural muscle function are dynamic in nature, the amount of pressure subjects will have to apply to the ground to accomplish the tasks must change. Quantifying the amount of force the subject applies to the ground may better inform us how well they are doing a particular task.

Delivering an acute intermittent hypoxia or a sham procedure

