Subjects will rest and be asked not to ingest any food or drink other than water for 30 minutes after the delivery of acute intermittent hypoxia, because fullness of the stomach may impede full depression of the diaphragm and compromise maximal respiratory measures. Following this, maximal inspiratory pressure, maximal expiratory pressure, forced vital capacity, mouth occlusion pressure, postural strength assessments, Neuromuscular Recovery Scale components, and assessments of ambulation will be reassessed as outlined above. EMG electrodes, electrogoniometers, and pressure sensors will be worn during the acute intermittent hypoxia and rest period, and will be removed following the conclusion of all testing.

Following the procedures for each visit, a \$75.00 gift card or check will be provided to participants. Thus, upon full completion of two visits, subjects will have been provided with \$150.00 following their participation in the study. If participants are asked to come in for a third session, an additional \$75.00 will be provided.

No standard therapies for people with SCI currently include acute intermittent hypoxia. Thus, this research does not intend to directly deliver therapeutic benefits to subjects. Rather, this research seeks to determine the therapeutic potential of acute intermittent hypoxia on respiratory strength and postural muscle function for people with SCI. As an alternative to participating in this study, subjects may not enroll or choose to withdraw at any time.

Statistical Plan

Percent changes in maximal inspiratory pressure, maximal expiratory pressure, forced vital capacity, mouth occlusion pressure, EMG parameters, spine and hip angles, postural strength measures, absolute Neuromuscular Recovery Scale scores, and assessments of ambulation will be compared pre- and post-intervention for both experimental conditions. Changes for each subject will be averaged, and the group mean change \pm standard deviation will be reported and compared across experimental conditions. Statistical differences between the group means for each variable in each experimental

condition will be compared using t-tests. Multiple comparisons will be accounted for. Statistical analyses will be carried out by the study investigators.

Acute Intermittent Hypoxia Safety Profile

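### Percent change is the tested variable for joint angles, EMG parameters and seated strength, where it can hinge on an arbitrary zero or be undefined, and no rule covers a zero pre-test

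*Combined protocol and SAP*

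**What the plan says.** The Statistical Plan (Section 6) opens its list of analysed quantities with "Percent changes in maximal inspiratory pressure, maximal expiratory pressure, forced vital capacity, mouth occlusion pressure, EMG parameters, spine and hip angles, postural strength measures". The list then changes wording: "absolute Neuromuscular Recovery Scale scores, and assessments of ambulation will be compared pre- and post-intervention". Changes are averaged over participants, and the mean and SD "will be reported and compared across experimental conditions". The test is a t-test; paired or unpaired is not stated. The Neuromuscular Recovery Scale is explicitly on an absolute scale. Ambulation, which follows it, can be read either way.

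The outcomes are described elsewhere in Section 6:

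- **Angles (item 5).** Electrogoniometers allow "quantification of the angle of the spine or hips achieved during each task". No reference position, sign convention or summary rule (peak, mean, range) is given. With the other sensors they "will be worn during the acute intermittent hypoxia and rest period, and will be removed following the conclusion of all testing", so they are fitted afresh at the next visit.
- **EMG (item 4).** EMG is to show "timing and amplitude of muscle activation as well as the frequency content of the EMG signal". It will also show when muscles are active, "as well as when certain muscles fire in relation to one another". The Statistical Plan does not say which parameters are tested.
- **Seated strength (item 3b).** The outcome is the dynamometer force at which unsupported sitting fails. No entry is given for someone who cannot sit unsupported before force is applied.
- **Population (Inclusion criteria).** "SCI affecting segments between C4-T12", with no criterion on completeness of injury or sitting ability.

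No section says what happens when a pre-test is zero, near zero, negative or unobtainable. Each visit has its own pre-test (Overview). Thirty participants are to be enrolled, with no SD, baseline, effect size or power stated.

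**The concern.** Percent change is 100 × (post − pre) / pre. It is interpretable only if the measure has a true zero and the pre-test stays well away from it. Two different failures are possible here.

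- **Arbitrary zero.** This affects a joint angle read as an absolute value and any signed timing of one muscle relative to another. Where zero is placed is a convention, yet it sets the denominator.
- **True zero, small pre-test.** This affects seated force and EMG amplitude. A severely impaired participant can have a very small denominator or none.

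Seated strength, and muscle activation in postural tasks, are Aim 2 outcomes. A result could turn on sensor zeroing or on one participant's tiny pre-test. If undefined ratios are dropped, the most impaired participants leave the analysis. If the rule is chosen after the data are seen, the investigators, who run the analysis themselves, choose the scale of the result.

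**Working it through.** **Inputs.** From the documents: 30 participants, two visits, pre- and post-tests at each visit, percent change, t-tests. Assumed throughout: paired t-test, two-sided 5%, and the SDs, baselines and effects named at each step. The plan has no power figure to reproduce. Power figures are simulated unless a formula is shown.

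**1. Arithmetic of the scale (illustrative values).**

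| Change | Pre-test | Percent change |
|---|---|---|
| Angle, +5 degrees | 5 / 30 / 90 / 175 | 100 / 16.7 / 5.6 / 2.9 |
| Same movement as x, or as 180 − x | 30→35, or 150→145 | +16.7, or −3.3 |
| EMG onset 20 ms earlier | 200 / 20 / −20 / 0 ms | −10 / −100 / +100 / undefined |
| Seated force, +2 units | 50 / 20 / 0.5 / 0 | 4 / 10 / 400 / undefined |

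Leverage: 29 participants gain 10% and one goes from 5 to 15 units (200%). The mean is (29 × 10 + 200)/30 = 16.3% and the SD is (200 − 10)/√30 = 34.7 points.

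If a share p of participants has a zero pre-test, the chance of at least one undefined ratio is 1 − (1 − p)^30. This is 45%, 79% and 96% for p = 2%, 5% and 10%.

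**2. Absolute angle, moving only the zero.** Assumed: effect 3 units, measurement SD 3, between-person SD 10. Each participant contributes four readings, so the SD of the difference in change is 3 × √4 = 6. The noncentrality is 3/(6/√30) = 2.74, which gives about 75% power wherever zero lies.

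| Mean pre-test | 90 | 60 | 30 | 15 | 0 |
|---|---|---|---|---|---|
| Power, percent change | 74% | 73% | 55% | 10% | 2% |
| Power, change in degrees | about 75% | about 75% | about 75% | about 75% | about 75% |

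Adjusting for the pre-test gives 96% if zero is the same at both visits. It gives about 85%, 79% and 76% if zero shifts between visits with SD 3, 5 and 10. If angles are excursions (mean 40, 30 or 20; SD 30% of the mean), percent change gives 64%, 60% and 54%, against 75–76% for plain change.

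**3. Seated force.** Assumed: 10% gain, most baselines 30–70 units, and 10/20/30% of participants with low baselines.

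| Low baselines | Additive noise SD | Percent change | Plain raw change |
|---|---|---|---|
| 2–8 | 3 | 23/8/5% | 98/95/88% |
| 8–15 | 3 | 65/45/32% | 98/95/90% |
| 15–25 | 3 | 89/79/70% | 98/97/94% |

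The loss shrinks with smaller noise. With low baselines 2–8, percent change gives about 59/34/22% at noise SD 1.5 and 82/61/46% at SD 1. With low baselines 8–15 and SD 1 it gives 100/100/99%.

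Under 12% proportional noise with low baselines 2–8, percent change holds at 54–55%. With 30% of participants low and visit-to-visit SD 0/10/20/30%, adjusted original units give 68/53/44/40% and adjusted logs 83/69/60/57%. The largest loss from original units is therefore 55 − 40 = 15 points.

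Readings were floored at 0.5 in the additive runs, so no exact zero was simulated.

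**4. Respiratory measures.** Assumed: 10% gain, 12% proportional noise. Percent change gives 55–56%. Adjusted logs give 83%, 69% and 57% at visit SD 0, 10% and 30%. At 5% noise there is no difference.

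**5. No true effect.** Hypoxia versus sham on percent change rejects 4.8–5.5% under proportional noise and 1–4% under additive noise with near-zero baselines. A pre-to-post test within sham alone rejects 6%, 7%, 8% and 16% at noise CV 8%, 12%, 20% and 35%, because noise in the denominator pushes mean percent change upward. That bias is common to both conditions and cancels between them.

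**6. Ambulation.** Ten metres in 20 s improving to 16 s is −20% as time and +25% as speed. On the log scale it is −0.223 or +0.223, the same size either way. A pre-test of 0 chair stands has no percent change.

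**The case against.** The best defence is that validity is intact, much of the affected material is optional, and this is a pilot with no power claim.

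**What stands.**

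- The hypoxia-versus-sham error rate is not inflated, and percent change is well defined for all four Aim 1 pressure and volume measures.
- Angle sensors and walking tests are worded as optional. Walking tests are limited to people who can attempt them safely, so zero chair-stand counts are less likely.
- No signed EMG parameter is named. Signed timing is one natural reading of relative firing.
- The severe seated-force figures use noise SD 3 on baselines of 2–8, which is 38–150% of baseline. With milder inputs the loss is small. For angles with mean pre-test 90 or 60, almost nothing is lost.
- Someone who cannot sit unsupported may be untestable rather than zero. Original units recover nothing for a missing value.

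A reader might infer from Section 7 that some participants are expected to need help in seated tasks. The text only permits assistance for safety. The possibility of near-zero force rests on the absence of any minimum trunk function in the inclusion criteria.

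**What does not stand.** Pilot status supplies neither the definitions nor a zero rule. With 30 participants, one extreme ratio can drive a mean.

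**Conclusion.** The point holds as a fault in the stated analysis scale for some outcomes, and it should be fixed. For absolute angles and signed EMG timing, the tested quantity depends on a convention that the plan does not fix. For seated force and low-amplitude EMG, it can be undefined or dominated by one participant. These conclusions follow from the formula and the text and need no assumed number.

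The size is uncertain. The fall from about 74% to 2% for angles, and the seated-force losses, come from assumed SDs and baselines and a paired t-test.

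Three stronger readings are tempting but unsupported:

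- **That the trial risks false positives for hypoxia versus sham.** Rejection stays at about 5% or below. Only separate within-condition tests are distorted.
- **That percent change is wrong throughout.** For the respiratory measures it is valid, and the gain from adjusted logs is precision alone.
- **That the angle outcome is necessarily arbitrary.** If it is an excursion from a fixed start, percent change is defined. The plan does not say which is meant.

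**What to change.** In the Statistical Plan:

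- **(a) Inferential test.** Make hypoxia versus sham the inferential test. Analyse each participant's difference in post values (hypoxia visit minus sham visit), adjusted for the difference in same-visit pre-test values.
- **(b) Scale per outcome, fixed in advance with no data-driven switch.** Original units: joint angles, EMG timing, seated force, chair stands. Log scale: inspiratory and expiratory pressure, vital capacity, mouth occlusion pressure, EMG amplitude (with a pre-stated noise-floor value), EMG frequency, Timed Up and Go, 10-meter walk.
- **(c) Definitions.** Define each angle as absolute or as an excursion from a stated start. State whether a participant who cannot sit unsupported is scored zero or recorded as untestable.
- **(d) Percent change.** Report it descriptively only, and draw no conclusions from separate within-condition pre-to-post tests.

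**Cost.** Wording and a few definitions; no new data, since each visit already has a pre-test. Results become less directly comparable with earlier percent-change reports, such as the 82% ankle-torque gain cited in the Background; the descriptive percentages soften this. For seated force, original units keep zero pre-tests in the analysis but can lose up to about 15 points of power if noise is proportional and visits vary a lot. A rule that uses logs unless some value falls below a floor does not remove that loss. In the same assumed scenario, a floor of 5 units triggers original units in over 90% of trials and a floor of 3 in 53–97%.

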This pilot study will utilize a single blind, placebo-controlled, randomized, repeated measures experimental design. Participants will be asked to come in for two visits at least 7 days apart. If study procedures are not completed in the two sessions (such as due to equipment malfunction or unexpected time restrictions/events), an additional session may be required to complete procedures. This will be scheduled at the participant's convenience. Participants will be asked to wear comfortable, casual clothing for participation ahead of time, during their phone screening. In the first visit, participants will be asked to complete a demographic health and function questionnaire. Questions may address their injury level, medical history, impact of their condition on physical functioning, breathing function, and their walking or other functional abilities. Participants may then be asked to undergo standardized assessments of muscle strength and sensory function. Following collection of this baseline information, the remainder of the first visit will be similar to all subsequent visits. Visits will include:

- Pre-assessments of respiratory strength, postural strength and function, EMG of trunk muscles, and trunk positioning using non-invasive sensors. For subjects who can stand or walk with assistance, ambulation assessments may be conducted while also recording trunk and lower extremity EMGs, and joint angles or forces using non-invasive sensors.
- 15 short exposures to hypoxic air, or a sham exposure, in a randomized order (details below)
- Post-assessments of respiratory strength, postural function, ambulation, EMG of trunk muscles, and trunk and joint positioning using non-invasive sensors

Each session will last about 3 hours and no longer than 6 hours. Rest breaks will be provided at regular intervals and at any time the participant requests. A study clinician will oversee the study procedures and monitor the participants, including a baseline assessment of vital signs (blood pressure, heart rate, and blood oxygen saturation) for safety.

For participants who provided consent for photography and/or video, recordings or photographs may be obtained during their session. Recordings or photographs will only occur based on the consent provided by each participant. The participant will be informed that they may refuse the use of photography or video recordings at any time during the procedures.

Study Procedures

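### Hypoxia and sham are compared on percent change with no pre-test covariate; regressing the log post-test difference on the log pre-test difference would usually be more precise, by an amount the documents do not fix

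*Combined protocol and SAP*

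**What the plan says.** The Statistical Plan in section 6 sets the scale of comparison as "Percent changes in maximal inspiratory pressure, maximal expiratory pressure, forced vital capacity, mouth occlusion pressure", followed by EMG parameters, joint angles and postural strength. The Neuromuscular Recovery Scale is treated differently: "absolute Neuromuscular Recovery Scale scores, and assessments of ambulation will be compared pre- and post-intervention for both experimental conditions". The summary step is "Changes for each subject will be averaged, and the group mean change" with its standard deviation, and the means for each experimental "condition will be compared using t-tests". No covariate or model is named, and the plan does not say whether the t-tests are paired.

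The Overview in section 6 gives the design: "This pilot study will utilize a single blind, placebo-controlled, randomized, repeated measures experimental design". On visits it says "Participants will be asked to come in for two visits at least 7 days apart". Each visit starts with "Pre-assessments of respiratory strength, postural strength and function, EMG of trunk muscles", then has "15 short exposures to hypoxic air, or a sham exposure, in a randomized order", then the post-assessments. So a participant who completes both visits supplies a pre-test and a post-test under each condition.

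The enrolment target in section 6 is 30. No effect size, standard deviation, correlation, alpha or power is given.

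**The concern.** A percent change divides the post-test by the same-visit pre-test. On the log scale it subtracts the whole log pre-test, measurement error included, as if the post-test tracked it one for one. If a person's pre-test happens to be low at the hypoxia visit, part of the return to their usual level is counted as a gain under hypoxia. Randomized order makes such errors cancel on average, but they still add variance.

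The pre-test precedes exposure, and section 8 expects any response to fade within four hours, while visits are at least 7 days apart. On the protocol's own account, then, the difference between a person's two pre-tests reflects chance or period and not treatment. That makes it a sound covariate.

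At stake is the precision of the hypoxia-versus-sham comparison on which Specific Aims 1 and 2 rest.

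**Working it through.** **Inputs.** From the documents: two visits per person, a pre-test and post-test at each, randomized order, n = 30. The enrolment figure has no derivation, so there is no planned power to reproduce. Assumed: equal pre-test and post-test variances s² on the log scale, complete pairs, paired t-tests, two-sided 5%, and the correlations below.

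**Step 1: variances.** For each person let Dpost and Dpre be the hypoxia-minus-sham differences in log post-test and log pre-test. Let rw be the pre-post correlation within a visit and rb the correlation between any two measurements at different visits.

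- Var(Dpre) = Var(Dpost) = 2s²(1 − rb)
- Corr(Dpre, Dpost) = b = (rw − rb)/(1 − rb)
- Change score: Var(Dpost − Dpre) = 4s²(1 − rb)(1 − b) = 4s²(1 − rw)
- Adjusted: Var(Dpost given Dpre) = 2s²(1 − rb)(1 − b²)
- Ratio, change score to adjusted = 2/(1 + b)

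The correlation that matters is b, between within-person differences. The ordinary between-person pre-post correlation can be high while b is low.

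**Step 2: cost of estimating the slope.** The adjusted variance is multiplied by 1 + 1/(n − 3) = 1 + 1/27 = 1.037. A balanced sequence term makes this 1 + 1/(n − 4) = 1 + 1/26 = 1.038, which hardly alters the results. Break-even with 1.037 is b = 2/1.037 − 1 = 0.93.

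**Step 3: results at n = 30.** The ratio is 2/(1 + b)/1.037, and the equivalent n is 30 times that. The last column supposes that the change-score test has 80% power (noncentral t, 29 df for the change score, 28 df for the adjusted analysis without a sequence term).

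| b | Variance ratio | Equivalent n by change score | Power if change score has 80% |
|---|---|---|---|
| 0 | 1.93 | 57.9 | 97% |
| 0.3 | 1.48 | 44.5 | 93% |
| 0.5 | 1.29 | 38.6 | 89% |
| 0.7 | 1.13 | 34.0 | 85% |
| 0.9 | 1.02 | 30.5 | 80.5% |
| 0.95 | 0.99 | 29.7 | 79.5% |
| 1 | 0.96 | 28.9 | 78.5% |

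**Step 4: check on percent change itself.** Step 1 is on the log scale, so 20,000 trials per case were simulated with lognormal outcomes, n = 30, a true log effect of 0.10 and assumed standard deviations. Power of the paired t-test on percent change against the log regression:

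- b = 0: 41% against 69%
- b = 0.27: 53% against 71%
- b = 0.5: 71% against 81%
- b = 0.73: 91% against 93%

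At b = 0.5 the t-test on log change also had 71% power, so the log-scale algebra describes the percent-change test well here. With no true effect at b = 0.5, rejection rates were 5.2% for percent change and 4.8% for the regression.

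**Step 5: which mixed model gives the same answer.** A random-intercept model with a single visit pre-test term blends the within-person slope b with the between-person slope (rw + rb)/(1 + rb). Simulated at n = 30:

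| (rw, rb) | b | Fitted slope, mixed model | Variance ratio, difference regression | Variance ratio, mixed model |
|---|---|---|---|---|
| (0.95, 0.80) | 0.75 | 0.94 | 1.10 | 1.05 |
| (0.95, 0.90) | 0.50 | 0.94 | 1.28 | 1.06 |
| (0.90, 0.85) | 0.33 | 0.88 | 1.48 | 1.12 |
| (0.90, 0.90) | 0 | 0.88 | 1.96 | 1.13 |

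The between-person slopes here are about 0.95 to 0.97, which pulls the fitted slope towards 1 and loses much of the gain: about half in the first row and more in the others.

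**Step 6: fewer complete pairs.** With 10 pairs the factor in Step 2 is 1 + 1/7 = 1.143. Break-even falls to 2/1.143 − 1 = 0.75, and the loss at b = 1 rises to 1 − 1/1.143 = 12.5%.

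**The case against.** The strongest reply is that this is an efficiency preference in a self-described pilot that claims no power. That stands. A reader might infer that the planned comparison is biased or inflates type I error. The documents do not support this: condition order is randomized, and the null simulation kept the percent-change test near 5%.

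A reader might also infer that adjustment is always better, or that the gain is as large as the b = 0 row. Neither follows. At n = 30 the gain disappears above b of about 0.93. A b of 0 requires same-visit tests to be no more alike than tests at least a week apart. The protocol also permits up to 10 trials of each respiratory test to secure a maximal effort, with rest as needed. That should reduce pre-test noise in MIP, MEP and FVC, though not remove it.

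It is tempting, too, to say that the plan fixes the slope at 1 on the measured scale. It does not: percent change imposes proportionality, which is a slope of 1 only on the log scale. The argument also does not reach the Neuromuscular Recovery Scale, which is listed as absolute scores.

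Two practical objections stand and shape the fix. Seated force could be zero, because eligibility sets no limit on completeness of injury and force is recorded when balance is lost; logs then fail. And 30 is an enrolment aim, with participants free to decline any procedure, so some outcomes may have fewer complete pairs.

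**Conclusion.** The point holds as a conditional gain in precision. The plan discards information that it already collects, and adjustment is the more precise analysis over most of the plausible range of b. The trade-off at 30 pairs is lopsided: a variance ratio of up to about 1.9 in favour of adjustment, against an efficiency loss of at most about 4%. With fewer pairs the possible loss is larger.

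The direction is well supported for b clearly below 0.93. The size is not, because every correlation, standard deviation and power figure used here is assumed. The calculations also take the t-tests as paired; that the plan does not say so is a separate gap. This is a recommended improvement and not a defect that invalidates the planned comparison.

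**What to change.** Amend the Statistical Plan before unblinded analysis:

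- For MIP, MEP, FVC, P0.1, and seated force where no zeros occur, regress each person's hypoxia-minus-sham difference in log post-test on the same difference in log pre-test, with a centred sequence term to absorb any period effect.
- Report the back-transformed intercept as the hypoxia-to-sham ratio with its 95% CI. Keep mean percent change and its standard deviation as a descriptive column.
- If a mixed model is preferred, fit person as a fixed effect, or split the pre-test into the person mean and the within-person deviation. Do not use a random intercept with one visit pre-test term.
- Report the number of complete pairs for each outcome.

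The cost is wording plus two degrees of freedom, one for the slope and one for period: 27 residual degrees of freedom with 30 pairs, instead of 29. No new data are needed.

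### Each participant receives both hypoxia and sham, but the Statistical Plan does not state a paired comparison and does not commit to reporting the within-person effect or its precision

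*Combined protocol and SAP*

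**What the plan says.** The Overview in Section 6 (Research Plan) sets the design: "This pilot study will utilize a single blind, placebo-controlled, randomized, repeated measures experimental design". It continues: "Participants will be asked to come in for two visits at least 7 days apart". Among the contents of each visit it lists "15 short exposures to hypoxic air, or a sham exposure, in a randomized order". The word crossover is not used, but two visits with the condition order randomized means that each person serves as their own control. Enrolment is stated earlier in Section 6: "We aim to screen 40 individuals with SCI and enroll 30 subjects in this study". No effect size, SD, alpha or power accompanies that number.

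Under the Statistical Plan, participants' changes are averaged, and the mean change with its "standard deviation will be reported and compared across experimental conditions". The test is given in one sentence: "Statistical differences between the group means for each variable in each experimental" "condition will be compared using t-tests". The plan adds that multiplicity will be handled, without naming a method. Neither the Statistical Plan nor any other section says whether the t-tests are paired, defines a per-person hypoxia-minus-sham difference, or mentions a confidence interval, an SD of differences or a within-person correlation.

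**The concern.** Specific Aims 1 and 2 ask whether hypoxia improves outcomes relative to sham. With both conditions in the same people, the direct answer is the mean of the individual differences, and its error comes from the spread of those differences. The plan's stated summary is instead one mean and one SD per condition. Each SD describes spread between people within a condition and says nothing about how a person's two responses move together.

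Two things are at stake. If the t-tests are run as the wording literally reads, as a comparison of two group means, the analysis discards the benefit of the within-person design. Whichever test is run, the stated output does not tell a reader how precisely the effect was estimated. In a pilot with an unpowered sample, that makes it hard to separate a result that excludes a worthwhile effect from one that is merely imprecise.

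**Working it through.** **Inputs.** From the documents: 30 participants, two conditions per participant, and mean change with SD per condition. Not in the documents, so assumed: an SD of 20 points of change in each condition, correlation r from 0 to 0.8 between a person's two changes, 30 complete pairs, and two-sided 95% intervals. The plan offers no calculation of its own to reproduce.

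**Step 1: SD of the paired difference.** In general, SD_d = sqrt(SD1² + SD2² − 2·r·SD1·SD2). With equal SDs this is 20 × sqrt(2(1 − r)). The term in r cannot be obtained from the two condition SDs.

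**Step 2: paired 95% CI half-width.** t(0.975, 29) × SD_d / sqrt(30) = 2.045 × SD_d / 5.477.

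**Step 3: half-width if the conditions are treated as independent.** t(0.975, 58) × 20 × sqrt(2/30) = 2.002 × 20 × 0.2582 = 10.3 points, whatever the value of r.

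| r | SD_d | Paired half-width | Independent half-width | Ratio (independent / paired) |
|---|---|---|---|---|
| 0 | 28.3 | 10.6 | 10.3 | 0.98 |
| 0.3 | 23.7 | 8.8 | 10.3 | 1.17 |
| 0.5 | 20.0 | 7.5 | 10.3 | 1.38 |
| 0.6 | 17.9 | 6.7 | 10.3 | 1.55 |

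At r = 0 the paired interval is slightly the wider of the two, only because it has 29 rather than 58 degrees of freedom.

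**Step 4: can the choice change a conclusion?** Take an assumed mean difference of 8 points with the same condition SDs.

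- Unpaired: t = 8 / (20 × 0.2582) = 8 / 5.16 = 1.55 on 58 df, p = 0.13 at every r.
- Paired, r = 0: t = 8 / (28.3 / 5.477) = 1.55 on 29 df, p = 0.13; 95% CI −2.6 to 18.6.
- Paired, r = 0.5: t = 8 / (20.0 / 5.477) = 2.19, p = 0.037; 95% CI 0.5 to 15.5.
- Paired, r = 0.8: SD_d = 20 × sqrt(0.4) = 12.6, t = 3.46, p = 0.002; 95% CI 3.3 to 12.7.

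The condition means and SDs that the plan would report are identical in all these cases.

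**The case against.** **The plan is silent; it does not exclude a paired analysis.** Nothing rules out paired t-tests or a confidence interval, and the description of the design as repeated measures points towards pairing. This stands. A reader might infer that the trial will use an unpaired test or will leave the interval out. The documents support only that it does not commit to either.

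**A paired test would let the precision be recovered.** This is true if the t statistic, or an exact unadjusted p-value, is published with the number of pairs. For example, a difference of 8 with n = 30 and t = 2.449 gives SD_d = 8 × 5.477 / 2.449 = 17.9. But the plan promises neither pairing nor those outputs, and a p-value adjusted by an unnamed method would not serve.

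**Mean and SD per condition is ordinary description.** Agreed. It is not an error, and it should stay. The gap is that nothing beyond it is specified as the effect estimate.

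**The harm may be small.** This also stands. The outcomes are pre-to-post changes, which already remove much of the stable difference between people, so a low correlation is possible. Near r = 0 the two intervals almost coincide.

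**The pilot label may suggest more than is there.** A reader might infer that the trial will fail to supply the SD for a follow-on study. No section describes such a study or gives this pilot the task of sizing one, and a parallel-group successor could use the per-condition SD of change. Nor do the documents say that conclusions will rest on p-values alone.

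**Conclusion.** The point holds as a gap between design and analysis. The design gives a within-person comparison; the Statistical Plan describes group means, condition SDs and t-tests of unstated type, and commits to no estimate of the within-person effect with its precision. The condition summaries alone cannot supply that precision.

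Under the assumptions above, an unpaired reading widens the interval by a factor of 1.17 at r = 0.3 and 1.55 at r = 0.6, and makes almost no difference at r = 0. With an 8-point difference it can turn p = 0.037 (r = 0.5) or p = 0.002 (r = 0.8) into p = 0.13. The SD, the difference and the correlations are illustrative; the documents give none of them.

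The half-widths are also best cases for 30 enrolled. Section 6 lets participants decline any part of the study, and the ambulation tests apply only to those who can safely attempt them, so some outcomes will have fewer pairs. The change is worth making before analysis, but the gap does not invalidate the trial.

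**What to change.** Amend the Statistical Plan so that, for each outcome:

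- the main result is the within-person hypoxia-minus-sham difference in change, on the change scale that the plan already uses for that outcome;
- it comes from a paired analysis that is named in advance: a paired t-test, or a mixed model with participant, condition and period. The model has the advantage of accounting for the randomized order of the two visits;
- it is reported with its 95% CI, the SD of the differences and the number of complete pairs;
- condition means and SDs remain as description;
- interpretation rests on the interval, not on the p-value alone.

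The cost is a few sentences in the Statistical Plan and some added table entries. No data, visits or procedures change.
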